### 5.4 Laboratory procedures

All analysis of clinical trial samples will be carried out in compliance with Good Clinical Laboratory Practice (GCLP). A laboratory analytical plan will be made available to all investigators before study start in order to harmonize procedures across participating centers. Beside prioritizing sub-studies, the laboratory committee will take the lead on administering the laboratory procedures and drafting the laboratory analytical plan.

# 6. STUDY INVESTIGATIONAL PRODUCT

No investigational product will be assessed during this study. The intervention consist of interrupting antiretroviral therapy in HIV positive participants identified to have low viral reservoir.

# 7. SAFETY ASSESSMENT

### 7.1 Adverse events

Safety of the intervention will be evaluated by recording Adverse Events (AE's) and grading laboratory and vital signs evaluations.

### Definition of an Adverse Event

An Adverse Event (AE) is generally described as any untoward medical occurrence in a subject or clinical investigation subject administered a pharmaceutical product and that does not necessarily have a causal relationship with this treatment. An AE can therefore be any unfavorable and unintended sign (including an abnormal laboratory finding), symptom, or disease temporally associated with the use of a medicinal (investigational) product, whether or not related to the medicinal (investigational) product.

However, this definition does not entirely fit the purpose of this study, because we will not assess a pharmaceutical product. Therefore, we will consider the intervention (=interruption antiviral treatment) as the pharmaceutical product under investigation and will adapt the definition accordingly:

An Adverse Event (AE) is generally described as any untoward medical occurrence in a subject or clinical investigation subject with treatment interruption and that does not necessarily have a causal relationship with the treatment interruption. An AE can therefore be any unfavorable and unintended sign (including an abnormal laboratory finding), symptom, or disease temporally associated with the treatment interruption, whether or not related to the treatment interruption.

Once treatment interruption has started, until the end of study, clinic staff will enquire about common possible side effects based on the "division of AIDS table for grading the severity of adverse events (see annex)" and will ascertain the occurrence of any adverse events since the last visit. All of them, including clinically significant laboratory abnormalities, will be recorded in the electronic Case Record Form (eCRF) and categorized in terms of severity, relationship to ARV interruption, outcome and seriousness, throughout the study duration. Episodes of viral acute syndrome, possible events of special interest, all serious adverse events (SAEs) and all the events leading to participants' withdrawal from the study will be monthly communicated to the Scientific Advisory Board.

All the events will be followed up till resolution, except those at the final end of study (=end of follow-up period).

### Severity, relationship of event to ARV interruption and outcome

- 1. *Mild:* events require minimal or no treatment and do not interfere with the subject's daily activities.
- 2. *Moderate:* events result in a low level of inconvenience or concern. Moderate events may cause some interference with functioning.

- 3. *Severe:* events interrupt a subject's usual daily activity and may require systemic drug therapy or other treatment. Severe events may be temporarily incapacitating.
- 4. Life-threatening: Subject at risk for death at the time of the event

### Assessment of causality

The investigator will assess the relationship between the ARV interruption and the occurrence of each AE/SAE. A list of expected adverse event is given. In addition, the investigator will use clinical judgement to determine the possible relationship of other (not expected) events.

The relationship of an adverse event to ARV interruption is to be assessed according to the following definitions and can only be done by the study physician:

- 1. **Definitely unrelated**: Reserved for those events which cannot be even remotely related to ARV interruption (e.g. injury caused by a third party).
- 2. Unlikely: There is no reasonable temporal association between the ARV interruption and the AE, the AE is not expected (according to a pre-defined list) and the event could have been linked to other known reasons.
- 3. **Possible**: The suspected AE may or may not follow a reasonable temporal sequence from ARV interruption but It is not fully unexpected but it could be linked to other known reasons.
- 4. Likely: The suspected adverse event follows a reasonable temporal sequence from ARV interruption. Either it is expected (according to based on the "division of AIDS table for grading the severity of adverse events) or it is likely caused by ARV interruption in the investigator's judgment.
- 5. **Definitely related**: Reserved for those events which have no uncertainty in their relationship to ARVs interruption.

### Outcome

The outcome of each AE must be assessed at the same visit and according to the following classification:

Completely recovered :	The participant has fully recovered with no
	observable residual effects
Not yet completely recovered :	Improvement in the participant's condition has occurred, but the participant still has some residual effects
Deterioration :	The participant's overall condition has worsened
Permanent damage :	The AE has resulted in a permanent impairment
Death :	The participant died due to the AE
Ongoing :	The AE has not resolved and remains the same as at onset
Unknown :	The outcome of the AE is not known because the participant did not return for follow-up (lost to follow-up)

### Serious Adverse Events

A Serious Adverse Event (SAE) is any adverse event/experience that results in any of the following outcomes:

- Death;
- Life threatening (subject at immediate risk of death);
- Requires participant hospitalization or prolongation of existing hospitalization;
- Results in congenital anomaly/birth defect;
- Results in a persistent or significant disability or incapacity;
- An important medical event that may not result in death, be life threatening, or require hospitalization may be considered an SAE when, based upon appropriate medical judgment, the event may jeopardize the subject's health and may require medical or surgical intervention to prevent one of the outcomes listed in this definition.

### Fast-track reporting

All SAEs will be compiled by the clinic supervisor on the paper report form for the corresponding visit. The Investigator will systematically check and validate the paper records on SAE and other points, and correct / complete as required before entering the data in the electronic CRF. The SAE will be registered as soon as treatment has been interrupted and up to the end of the study.

There may be situations when an SAE has occurred and the investigator has minimal information to include in the initial report to the pharmacovigilance. However, it is very important that the investigator always makes an assessment of causality for every event prior to transmission of the report to the pharmacovigilance. The investigator may change his/her opinion of causality in light of follow-up information, amending the SAE-report form accordingly.

All SAE's whether or not deemed related or expected must be reported immediately or within 24 hours (one working day) using the SAE Notification Form by telefax or email to:

Clinical Trials Unit Institute of Tropical Medicine [name] – Belgium [contact] Email: [contact]

The title of the e-mail/fax should mention the name of the study code, the patient code and the wording "SAE – Initial/follow up report".

Line listings of all reported SAE's will be sent at a monthly base to the joint SAB/CAB, IRB and local ECs. Due to no investigational medicinal product, there was agreed upon no SUSAR reporting (ref. [name] – FAGG).

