### 5.1.4 Leukapheresis

A leukapheresis will be scheduled between the enrolment visit and the baseline visit. The necessary sample will be transferred to the Virology Laboratory of ITM in order to perform a Viral Outgrowth Assay (VOA) at later time. More information on the VOA is to be found in section 5.3 of the protocol. When patients consent, all remaining samples will be kept locally at each site according to the procedure for the sample storage described in the laboratory analytical plan. These samples will be used later for sub studies as described in relevant amendments and in section 2.2 of this protocol.

If a site doesn't have the capacity to store samples locally, these may be transferred to the FAGG accredited biobank of BIMETRA at the UZ Gent. Samples will be kept for a maximum of twenty years after study completion. Remaining samples will be destroyed at the end of the storage period.

Procedure	Screening 1	Screening 2	Leukapheresis	comments
Eligibility				
Informed Consent 1	Х			
Informed Consent 2		Х		
Incl./Excl. Criteria	Х	х		
Medical History	Х			
ARV history	Х			
Plasma Viral load	Х			
Resistance Test	Х			
CD4-cell count	Х			
Concom.medications	Х			
Psych. Interview		Х		
Phys. Examination	Х			Full PE, incl. vital signs
Laboratory Tests				
Hemoglobin	х			
ANC	х			
Platelets	Х			
Ureum/Creatinin	х			
AST	х			
ALT	х			
HBs Ab	х			
HBc Ab	х			
HBs Ag	х			
HCv Ab	х			
Pregnancy Test	Х			
Reservoir Assessment				
Tot. HIV DNA	х			
Us RNA	х			if tot hiv DNA negative
VOA			Х	
Sample storage	Х		Х	

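### The operational AE/SAE rules start at treatment interruption and do not cover the research leukapheresis that precedes it

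*Protocol*

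**What the plan says.** Protocol 5.1.4 places the procedure: "A leukapheresis will be scheduled between the enrolment visit and the baseline visit". It supplies cells for the viral outgrowth assay. Protocol 5.3 says that the assay result plays no part in proposing interruption, and leftover material is stored for sub-studies. Treatment is stopped only after the baseline assessments (5.1.5).

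The safety rules are in Protocol 7.1. The adapted AE definition covers "any untoward medical occurrence in a subject or clinical investigation subject with treatment interruption". On collection: "Once treatment interruption has started, until the end of study, clinic staff will enquire about common possible side effects", and at each visit staff "will ascertain the occurrence of any adverse events since the last visit". On causality: "The investigator will assess the relationship between the ARV interruption and the occurrence of each AE/SAE". On serious events: "The SAE will be registered as soon as treatment has been interrupted and up to the end of the study". The notification sentence in the same section carries no start date of its own: "All SAE's whether or not deemed related or expected must be reported immediately or within 24 hours (one working day".

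SAP 4.2 reports AEs and SAEs from the start of interruption to the end of follow-up.

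**The concern.** Leukapheresis is done for research, and Protocol 4.3 (Step 5) itself calls it heavy. It is the most invasive study procedure before interruption, yet the rules for recording, grading, attributing and expediting adverse events all begin after it. If the plan is followed as written, a serious complication in an early participant need not be registered, linked to the procedure or notified within 24 hours while later participants are still being scheduled. What is at stake is participant protection and oversight, together with the ability to report afterwards what the procedure did.

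**Working it through.** **Order of events.** Second consent and enrolment (5.1.3), then leukapheresis (5.1.4), then the baseline visit, then interruption at its end (5.1.5). Leukapheresis therefore falls before interruption.

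**Where each rule starts.**

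| Rule | Starts at, or refers to | Requires capture of a leukapheresis event? |
|---|---|---|
| AE definition (7.1) | Subjects with interruption | No |
| AE enquiry (7.1) | Once interruption has begun | No |
| First look-back, week 2 (7.1, Table 2) | The last visit, which is baseline | No, the procedure is earlier |
| SAE registration (7.1) | Interruption | No |
| 24-hour SAE notification (7.1) | No start date given | Not excluded, but not required |
| Causality scale (7.1) | All five categories concern ARV interruption | No category for a procedure |
| Table 1 | Has a leukapheresis column | No AE or SAE row |
| Table 2 | AE and SAE rows first marked at week 2 | Baseline cell empty |
| SAP 4.2 | Start of interruption | No |

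SAP 2.3 speaks of the whole study period, but SAP 4.2 defines that as interruption plus follow-up. The tables were read from PDF, but the running text of Protocol 7.1 and SAP 4.2 is enough without them.

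**Other routes by which an event could surface.**
- The baseline re-check of criteria, medical history check, medication review, examination and laboratory tests (5.1.5).
- Unscheduled-visit records (5.1.10) and the evaluation at withdrawal (4.5).
- The monthly notice: "all the events leading to participants' withdrawal from the study will be monthly communicated to the Scientific Advisory Board" (7.1). A participant who recovers and continues would not trigger it.
- Three-monthly safety reports from the trials unit, and a formal meeting on all available safety data that the safety monitor may request once there is a major concern (7.3).
- The general duties in Annex 2 to monitor and document risks and to inform the ethics committee of serious events.

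Each could bring an event to someone's notice. None sets grading, attribution to leukapheresis or a 24-hour clock before interruption.

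**Number exposed.** The inputs are in Protocol 4.3, Steps 3 to 5: 643 screened, 7% qualifying, 30% drop-out.
- 643 × 0.07 = 45.0, matching the protocol's 45.
- 45 × (1 − 0.30) = 31.5, which the protocol gives as 32.

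Under 5.1.4 and Table 1, leukapheresis follows the second consent, so about 32 people have it. Step 5 describes those who reach the interruption decision as having already had it. If that means the procedure comes before drop-out, up to 45 are exposed, a difference of 45 − 32 = 13.

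**What full capture could show.** With no events, the 95% Wilson upper limit is z²/(n + z²), with z = 1.96:
- n = 32: 3.84/35.84 = 10.7%.
- n = 45: 3.84/48.84 = 7.9%.

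Capture would therefore serve case-by-case oversight more than precise rate estimation.

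**The case against.** The best defence is that the scope is deliberate. Protocol 7.1 explains that no product is under test, so interruption is treated as the product and the AE definition is adapted to it. Registration, causality, the tables and the SAP then follow consistently. This stands: the documents do not contradict themselves on the window. But the explanation justifies a definition centred on interruption. It gives no reason for leaving a research procedure outside the rules. Protocol 4.5 promises withdrawn participants care for complications whether or not study procedures caused them, so such events were foreseen, yet the causality scale has no place for them.

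A second defence is that a serious complication would probably surface. The baseline re-check takes in recent acute infection or serious illness and haemoglobin and platelet limits, and the undated 24-hour sentence lets a site report early. This also stands in part. A reader might infer that a complication would go unseen, or that the safety monitor can only ever look at SAE reports. The documents do not support either: there are several routes to notice, and 7.3 lets the monitor ask for all available safety data. That request, however, presupposes a major concern, which an unregistered event need not raise.

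A third objection is timing. The protocol text carries version 6.0 of May 2018, the SAP is dated July 2018, and the planned duration was 23 months, so many or all leukaphereses may already be done. The documents do not give enrolment status. This limits the prospective benefit but does not remove the reporting gap.

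**Conclusion.** The gap is real and should be closed. The operational AE/SAE rules do not require registration, grading, attribution or 24-hour notification of leukapheresis events before interruption, for about 32 people or up to 45 depending on how 4.3 is read. The leukapheresis-to-baseline interval is not fixed, so no length is claimed for the uncovered period.

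Two stronger conclusions are tempting. The first is that the trial's safety results would be biased. They would not: the safety endpoint concerns interruption, and events before it are properly outside those rates; the primary endpoint is also untouched. The second is a figure for the chance of a missed event. The documents give no leukapheresis event rate, any AE would have to be separated from a serious one, and some events would surface anyway, so no probability is claimed.

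The conclusion rests on the protocol and SAP alone. The safety monitor's Charter, the SAE Notification Form, the eCRF and the laboratory analytical plan are not available, and one of them could contain a wider instruction.

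**What to change.** 1. Start AE/SAE registration at the second informed consent, or at leukapheresis if that is earlier, and state that 24-hour SAE notification starts at the same point.
2. Add AE/SAE assessment to the leukapheresis column of Table 1 and the baseline column of Table 2.
3. Add a study-procedure attribution to the AE definition and the causality scale in Protocol 7.1.
4. In SAP 4.2, tabulate pre-interruption events separately, with everyone who had leukapheresis as denominator. Interruption rates stay as planned.
5. For anyone already apheresed, retrieve events from source, unscheduled-visit and withdrawal records, and state the capture window in the report.
6. Reconcile Protocol 4.3 (Step 5) with 5.1.4 on the order of leukapheresis and drop-out. Item 4 needs this to fix its denominator.

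The cost is a protocol amendment. If it is classed as substantial, Protocol 11.3 requires approval from every body that approved the protocol; by 11.2 these are the ITM review board, the Antwerp ethics committee and three site committees, 1 + 1 + 3 = 5. The eCRF change needs validation before use (10.3), and each participant has a short extra recording period. Retrospective retrieval may be incomplete. If all leukaphereses are already done, only items 4 to 6 apply.

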# 7.2 Scientific Advisory Board and Community Advisory Board

A merged scientific and community board will be composed of scientists with broad experience in the field of HIV clinical trials as well as members from patient organizations.

The main task of this board will be to advise the study steering committee on the onwards conduct of the study. The communication will preferably take place electronically.

Members will meet, preferably by means of teleconference, at least three times a year in order to be informed about the evolution of the study.

# 7.3 Independent Safety Monitor

A Data Safety and Monitoring Boards is not mandatory for this type of project, where there is not a pharmacological 'intervention'. However, to ensure an extra layer of independent supervision on safety issues, the Sponsor will appoint an independent data safety monitor, who is fully independent from the study team. He/she will receive and review all SAE reports on an ongoing basis. A Charter will be set up to describe the Safety Monitor role. The independent data safety monitor will be experienced in HIV medicine and clinical research. In case of major safety concerns, this independent safety data monitor may advise the sponsor to halt recruitment of the trial and/or request to organize a formal meeting with the TMG members with a complete overview of all available safety data."

Every three months, the CTU will provide safety and efficacy reports to the steering committee, relevant IEC's and members of the advisory board.

# **8. STATISTICAL METHODS**

The statistical analysis of the clinical trial will be performed according to a Statistical Analysis Plan which will be approved before database lock.

# 8.1 Study hypothesis

A small proportion, estimated at 5 to 15%, of participants identified to have a low proviral DNA in PBMC while on long-term ART will have a sustained viral suppression 48 weeks after analytical treatment interruption.

# 8.2 Variables of interest

The primary endpoint is the proportion of participants with undetectable viral load (<50 HIV RNA copies/ml plasma) 48 weeks after interruption of their antiretroviral treatment.

# 8.3 Statistical methods

### 8.3.1 Population to be analyzed

The statistical analyses will be performed on all enrolled participants.

# 8.3.2 Baseline characteristics

The number of participants screened, enrolled and excluded will be presented. Excluded participants will be summarized by reason for exclusion. For the participants enrolled in the study, the number discontinued or lost to follow-up will be tabulated by reason. This information will be summarized in a CONSORT flow diagram. Participants will be described with respect to baseline characteristics. The description will be done in terms of medians and interquartile ranges for continuous characteristics and using counts and percentages for categorical characteristics.

# 8.3.3 Primary objective/endpoint

The proportion of participants with undetectable viral load (<50 HIV RNA copies/ml plasma) 48 weeks after interruption of ART will be estimated together with a 95% Wilson confidence interval.

### 8.3.4 Secondary endpoints

Safety of interrupting ART will be evaluated based on AEs and SAEs percentages together with a 95% Wilson confidence interval.

Reservoir replenishment and HIV viral load kinetics following ART interruption will be summarized in terms of medians and interquartile ranges. If present, pVL rebound will be represented graphically with a spaghetti plot.

Potential predictors of post-treatment control will be assessed by Fisher's exact test at 5% significance level.

### 8.3.5 Subgroup analyses

No subgroup analyses will be performed.

### 8.3.6 Multiplicity and Missing Data

Complete-case analyses will be performed.

### 8.4 Sample size and power

It is estimated (section 4.3) that from all patients screened, 32 patients will finally enter the study and stop ART. Assuming a proportion of post-treatment control ranging between 5% and 15%, the width of the 95% Wilson confidence interval will be between 18 and 25 percentage points.

# 9. MONITORING AND QUALITY ASSURANCE

This study will be monitored according to the Monitoring SOP of the ITM Clinical Trials Unit, as agreed with the Sponsor. The PIs and research staff of the involved sites will allocate adequate time and resources for such monitoring activities. The investigators will also ensure that the monitor is given access to all the above noted study-related documents, the Case Report Forms and study-related facilities (e.g. diagnostic laboratory, etc.) and has adequate space, time and resources to conduct the monitoring.

The Principal Investigator at each site declares, by signing this protocol, that he/she will permit trial-related monitoring, audits either conducted by the Sponsor or externally requested, Independent Ethic Committee review and regulatory inspections providing direct access to source data/documents, relevant electronic systems and trial facilities.

The Principal Investigators and co-Investigators agree to conduct the present study in full agreement with the Declaration of Helsinki (October 2013)(see Appendix I) and the ICH Good Clinical Practice guidelines (1996).

# **10. DATA MANAGEMENT**

Data Management will be performed by the data manager at the CTU (ITM) and in collaboration with the study staff assigned for data management at the 4 sites (PIs, data entry clerks).

